### **Definition of serious adverse events**

An SAE is any untoward medical occurrence that at any dose:

- Results in death.
- Is life-threatening.
- Requires inpatient hospitalization or prolongation of existing hospitalization.
- Results in persistent or significant disability/incapacity.
- Is a congenital anomaly/birth defect.
- Is considered a clinically important medical event. The medical concepts included in Section 18.1 should be taken into account when applying this seriousness criterion.

An elective hospital admission, e.g., for pre-planned surgery, will not be considered an SAE if documented at enrollment. Short-lasting (<24 hours) hospital admissions, e.g., for clinical check-ups, not meeting any of the other above mentioned criteria will also not be considered SAEs.

### **Special procedures for serious adverse events**

If SAEs occur that are not tolerable, the investigator will decide whether to stop the trial participation and/or treatment of the subject. For further details, see Section 9.3.

### **Expectedness of adverse events**

Expectedness will be assessed by the sponsor.

An unexpected adverse event is one where the nature or intensity is not consistent with the information in the neridronic acid investigator's brochure.

Furthermore, reports that add significant information about the specificity or severity of a known, already documented adverse reaction constitute unexpected adverse events. For example, an adverse event more specific or more severe than expected would be considered "unexpected".

### **Definition of adverse drug reactions**

An adverse drug reaction is any untoward and unintended response to an IMP or a medicinal product related to any dose administered.

A list of adverse drug reactions seen for the IMP is given in the reference safety information (neridronic acid investigator's brochure).

### **Documentation of adverse events**

The subjects will be questioned about possible adverse events with non-leading questions before administration of the IMP and at regular intervals thereafter as defined in Section 1.6.

All adverse events reported spontaneously by subjects at any time point will also be documented.

All adverse events will be documented in the eCRF with the following information where appropriate:

- Description (adverse event reported term).
- Start date/time.
- End date/time or continuation.
- Whether adverse event was serious.
- Intensity.
- Outcome.
- Action taken with IMP.
- Countermeasures.
- Causal relationship to IMP.

### **Definition of intensity**

The clinical intensity of an adverse event will be classified as:

Mild:	Signs and symptoms that can be easily tolerated. Symptoms can be ignored and disappear when the subject is distracted.
Moderate:	Symptoms cause discomfort but are tolerable; they cannot be ignored and affect concentration.
Severe:	Symptoms which affect usual daily activity.

For adverse events where the intensity changes over time, the maximum intensity observed during the whole duration of the adverse event will be documented.

Adverse events occurring in the Enrollment Period but before first administration of an IMP and worsening on or after IMP administration will be documented as new adverse events.

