## 1.5 Statistical analyses

The primary analysis will be performed once all subjects have completed Visit 11 (Week 26), including database lock and unblinding. The results from this 26-week analysis will be reported in an interim integrated clinical trial report.

The final analysis of this trial, including Treatment Period B and Follow-up Period 2, will be performed after the last subject has completed the trial and the database has been locked.

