## 3.2 Definition of terms

Term	Definition
Allocated subjects	Enrolled subjects who are assigned to IMP.
Applicable regulatory requirement(s)	Any law(s) and regulation(s) addressing the conduct of clinical trials of IMPs of the jurisdiction where the trial is conducted.
CRPS Type I	Occurs after a minor or major tissue injury without clinical signs of major peripheral nerve injury.
CRPS Type II	Occurs after an injury with clinical signs of major peripheral nerve injury.
End of the trial	The trial-related end of the trial is defined as the date of last subject out. The subject-related end of trial is defined as date of last contact with the subject according to the protocol.
Enrolled subjects	Subjects who signed an informed consent form.
Enrollment failures	Enrolled subjects who were not allocated to IMP.
First subject allocated	First subject that was allocated to IMP.
First subject in	Date of first enrolled subject.
Investigational medicinal product	A generic term describing the preparation(s) under investigation in this trial, i.e., neridronic acid and placebo.
Last subject out	Date of last contact with the last subject according to the protocol.
Patient	Person under a physician's care for a particular disease or condition.
Screened subjects	Screened subjects are subjects undergoing screening. Screening is any activity concerning subjects who could potentially be enrolled into the trial before the informed consent form is signed.
Subject	Individual who participates in a clinical trial (healthy person or patient), either as recipient of an IMP or as control.
Treated subjects	Subjects with at least 1 administration of IMP.

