#### **Second treatment course**

For those subjects not experiencing sufficient efficacy after a first treatment course with IMP as assessed at Visit 11 (Week 26), a second treatment period (Treatment Period B) in subjects with

persistent pain is included to allow subjects previously on neridronic acid and on placebo to be treated with neridronic acid either for the second or the first time, respectively. The second treatment course is scheduled to occur after 26 weeks.

Subjects treated during Treatment Period B will provide data on safety and tolerability of a second treatment course as well as descriptive data on the efficacy of a second treatment course in subjects with no or insufficient response to the first treatment course as well as in subjects who lost response to the initial treatment course. Furthermore, subjects from the placebo group can receive verum treatment in Treatment Period B.

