##### 14.1.8.1 Adverse events

A definition of adverse event is given in Section 12.4.1.

The original terms recorded in the eCRF to identify adverse events will be coded using the most recent version of the Medical Dictionary for Regulatory Activities (MedDRA) at the time of database lock.

Adverse events are only considered treatment emergent adverse events (TEAEs) if they start after first administration of IMP. All adverse events occurring in a subject administered a trial treatment and which do not necessarily have a causal relationship with this treatment will be defined as TEAEs. In addition, pre-treatment adverse events which worsen during the treatment periods are also considered TEAEs.

Treatment emergent adverse events will be summarized.

An overview of the number and percentage of subjects with at least 1 TEAE, serious TEAEs, non-serious TEAEs, unexpected TEAEs, related TEAEs, related serious TEAEs, TEAEs leading to discontinuation from IMP, TEAEs leading to discontinuation from the trial, and deaths will be created.

The number and percentage of subjects with adverse events and the number and percentage of events will be summarized by System Organ Class and Preferred Term for TEAEs, serious TEAEs, non-serious TEAEs, and related TEAEs.

Additional summaries by intensity, causal relationship, outcome, countermeasure, time to onset, duration, and expectedness will be provided.

Subjects with SAEs and subjects with adverse events leading to trial/treatment discontinuation will additionally be listed.

The distribution of time to onset of any TEAE will be summarized using time-to-event methods if applicable. A graphical display using Kaplan-Meier methods displaying subjects at risk per time point will also be produced.

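### The rule for re-recording worsened adverse events stops at first IMP, so an event that worsens after the first Period B infusion keeps its earlier onset and takes the later intensity

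*Protocol*

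**What the plan says.** Section 12.4.1 lists what is kept for each adverse event: one start date and time, one end ("End date/time or continuation"), one intensity and one causality assessment. Under Definition of intensity, when the intensity of an event changes, "the maximum intensity observed during the whole duration of the adverse event will be documented". The only departure from one record per event follows directly and calls for a fresh entry: "Adverse events occurring in the Enrollment Period but before first administration of an IMP and worsening on or after IMP administration will be documented".

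Section 14.1.8.1 uses the same single anchor: "Adverse events are only considered treatment emergent adverse events (TEAEs) if they start after first administration of IMP". It adds that "pre-treatment adverse events which worsen during the treatment periods are also considered TEAEs".

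Section 3.2 defines IMP to cover both arms ("i.e., neridronic acid and placebo"). Section 8.1, Second treatment course, sets up a second start of exposure after Week 26, for a repeat course or for a first one: "Furthermore, subjects from the placebo group can receive verum treatment in Treatment Period B". Sections 1.2 and 1.5.3 ask for safety data from Treatment Period B and Follow-up Period 2 to be described separately, and by initial treatment for those treated in Period B. On timing, Section 1.5 states: "The primary analysis will be performed once all subjects have completed Visit 11 (Week 26), including database lock and unblinding".

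**The concern.** The recording rule suits a trial with one start of exposure; this trial has two. The sponsor already accepts the principle that a worsening after exposure begins deserves its own record, because it applies that principle at the first IMP administration. It does not apply it at Visit 11, where exposure to active drug begins for placebo-first subjects and begins again for neridronic-first subjects.

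Section 8.1 says that Period B subjects will supply data on the safety and tolerability of a second course, and Section 14.1.8.1 promises summaries by intensity, causal relationship, time to onset and duration. Each of those draws on fields that mix the time before and after Visit 11 when an event spans it. What is at stake is how clearly the trial can describe what happened to already ongoing events once open-label drug was given.

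**Working it through.** The plan states no figure on this point, and no sample size, power or event count enters it. The check is to apply the written rules to events around Visit 11.

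**Inputs**
- Record content, maximum-intensity rule and new-event exception: Section 12.4.1.
- IMP includes placebo: Section 3.2. A placebo subject's first IMP is thus the Visit 2 infusion.
- Treatment emergence: Section 14.1.8.1.
- Period B infusions at Visits 11 to 14, nominally Days 183 to 192: Sections 1.6.2 and 11.1.4.2.

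**Step 1: the rules applied**

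| Event | Record produced |
|---|---|
| (a) Starts in the Enrollment Period, worsens after IMP | New record with its own onset and intensity |
| (b) Starts after the first Visit 2 infusion, mild at Visit 11, severe after the first Period B infusion | One record: onset before Visit 11, intensity severe |
| (c) First appears after the first Period B infusion | New record with onset in Period B |

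Case (b) is the gap. It arises in both arms: first active exposure for placebo-first subjects, second course for neridronic-first subjects.

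**Step 2: does another rule cover case (b)?**
- Section 12.4.1, Definition of adverse events, turns a changed pre-existing condition into an adverse event, but only for conditions present before enrollment.
- Section 12.4.6 records clinically relevant changes since the previous visit as adverse events, but only for physical examination findings.
- Section 14.1.8.1 speaks of treatment periods in the plural, but its worsening clause is limited to pre-treatment events. It classifies events and creates no new record, onset or intensity.

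None of these covers a non-examination event that began after the first IMP administration.

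**Step 3: could later analysis repair it?** A record of type (b) holds one start date and one maximum intensity. The intensity before the switch and the date of worsening are not among its fields. Analysis rules can assign the record to a period but cannot split it.

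**Step 4: the 26-week tables.** The lock waits for the last subject's Visit 11. The last Period B infusion is nominally 192 − 183 = 9 days after Visit 11, so subjects who reached Visit 11 well before the last one may already have post-infusion intensities on file. Section 11.1.4.1.1 also has adverse events recorded after the Visit 11 infusion itself. Whether such values enter the 26-week tables depends on a data cutoff that this protocol does not state.

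**The case against.** Much can be said on the other side.

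- *The analysis plan can handle it.* Section 14.1.2 leaves full analysis details to the SAP, which is not at hand, and treatment emergence by period can properly be set there. That stands for the attribution rule. It does not reach the recording rule, which the protocol fixes and which decides what data exist.
- *Some information survives elsewhere.* The eCRF audit trail (Section 13.1) logs changed entries, a new or changed medication carries its own start date (Section 12.2.2), and serious events are reported separately. True, but none of these is a planned source for the intensity or onset summaries.
- *Investigators may record an acute phase reaction as a distinct event.* Section 8.2 describes it as self-limiting and usually over within 24 to 48 hours, and nothing in Section 12.4.1 prevents a separate entry. This narrows the problem but leaves the outcome to each site's judgement.

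Three stronger readings are tempting and not supported.

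- A reader might infer that such events vanish from the Period B summary. Sections 1.2 and 1.5.3 refer to data evaluated during that period, not to events with onset in it, so how ongoing events are counted remains open.
- A reader might infer that placebo intensity is inflated in the 26-week comparison. The cutoff is unstated, and any leakage would also raise intensities in the neridronic arm.
- A reader might want a count of affected subjects. The protocol gives no rate of Period B entry, of events ongoing at Visit 11 or of worsening, so any count would rest on invented rates.

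**Conclusion.** The gap is real and follows from the protocol's own wording. It is confined to adverse events that began after the first IMP administration, were ongoing at the first Period B infusion, worsened on or after it, and were not entered as separate events. For these, onset and intensity in Period B are not captured, which blurs the separate safety description of Period B by initial treatment. An effect on the 26-week safety tables is possible in either arm and depends on the data cutoff. Its size and net direction cannot be estimated from the document. The primary and confirmatory efficacy tests are untouched. The conclusion assumes that sites follow Section 12.4.1 as written and that no eCRF completion instruction, which we have not seen, already splits records at Visit 11.

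**What to change.** Extend the new-event sentence in Section 12.4.1: an adverse event ongoing at the first Treatment Period B infusion that worsens on or after that infusion is documented as a new adverse event with its own start date, and the original record keeps the maximum intensity reached before that infusion. Add a matching eCRF completion instruction. Assignment of treatment emergence by period should then follow, either in Section 14.1.8.1 or in the SAP.

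The cost is one protocol sentence, one instruction and a few more adverse event records. Event counts would rise slightly, while the number of subjects with any event over the whole trial would not change.

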### **Definition of outcome at the time of last observation**

The outcome at the time of last observation will be classified as:

- Recovered/Resolved.
- Recovering/Resolving.
- Not recovered/Not resolved.
- Recovered/Resolved with sequelae.
- Fatal.
- Unknown (unknown should only be used, if at the time of the last visit for a subject in a trial, the outcome of the adverse event is unknown to the investigator, e.g., because the subject is lost to follow-up).

### **Definition of countermeasures**

“Countermeasures” will be defined as:

None:	No countermeasure given.
Newly started medication:	A newly started medication or change in dose or route of application of a medication due to the adverse event (to be listed on the prior/concomitant medication page) that is used

---

as a countermeasure.

---

**Trial discontinuation:** It was necessary to discontinue the subject from the trial due to the adverse event.

---

**Other:** All other countermeasures, e.g., physical therapy, surgery.

---

Except for none, multiple countermeasures for 1 adverse event can be recorded.

Classification of action taken with IMP when an adverse event occurs:

- Dose not changed.
- Drug interrupted.
- Drug withdrawn.
- Not applicable.
- Unknown.

### Classification of causation

The causal relationship of an adverse event to IMP will be classified using the following terminology. The given criteria for each term are for consideration and are neither exhaustive nor required to be fulfilled in total for the selection of the respective term:

Terms for classification of causation	Criteria for the selection of causality classification terms
Conditional/ Unclassified:	Additional data for a proper assessment are under examination.
Unassessable/ Unclassifiable:	The available data cannot be judged because information is insufficient or contradictory, and cannot be supplemented or verified.
Not related:	Data with sufficient evidence to accept that there is no causal relationship to IMP administration (i.e., there is no temporal relationship to IMP administration or proved other cause).
Unlikely:	Data without sufficient evidence to accept that there is no causal relationship to IMP administration, but also with no evidence or argument to suggest a causal relationship (e.g., the temporal relationship to IMP administration makes a causal relationship improbable, and other drugs, chemicals, or underlying disease[s] provide plausible explanations).
Possible:	Data with limited evidence or argument to suggest a causal relationship (e.g., there is a reasonable time sequence to administration of the drug, but the adverse event could also be explained by concurrent disease[s] or other drugs or chemicals. Information on drug withdrawal may be lacking or unclear).
Probable/likely:	Data with sufficient evidence or argument to suggest a causal relationship (e.g., there is a reasonable time sequence to administration of the drug, the adverse event is unlikely to be attributed to concurrent disease[s] or other drugs or chemicals, and a clinically reasonable response on withdrawal [dechallenge]).
Certain:	Data with clear evidence for a causal relationship (i.e., a clinical event, including laboratory test abnormality, occurs in a plausible time relationship to drug administration, and it cannot be explained by concurrent disease or other drugs or chemicals. The response to withdrawal of the drug [dechallenge] should be well defined and clinically plausible, using a satisfactory rechallenge procedure if appropriate).

### **Follow-up of subjects with an adverse event**

Any adverse event or clinically relevant abnormal laboratory or vital sign result will be followed until it reaches a satisfactory resolution, or becomes stable, or clinical judgment indicates that further evaluation is not warranted.

### **Notification of serious adverse events**

All SAEs (including death, irrespective of cause during the trial, regardless of their relationship to IMP, must be reported as soon as possible but no later than 24 hours after learning of the event. Before any trial-related procedure is performed, the trial site must be provided with contact details at the sponsor's Drug Safety Department for this reporting.

The investigator must submit a report, called a safety reporting form, which includes a description of the event, the therapy instituted, and trial procedures. The following information should be communicated with the first notification of an SAE:

- Trial identifier.
- Subject's identifier.
- Subject's date/year of birth (if available, see local data protection requirements) or age (at adverse event onset).
- Subject's sex.
- First administration of IMP (date and time, if available).
- Last administration of IMP (date and time, if available).
- Adverse event verbatim term (specific diagnosis, if possible).
- Adverse event onset (date and time, if available).
- A brief description of the event, the course, and the countermeasures taken.
- Intensity.
- Seriousness criterion.
- Outcome.
- Concomitant medication at onset of the event and whether one of the concomitant medications is also suspected to have caused the event.
- Relevant history/pre-existing medical conditions.
- Investigator's assessment of the relationship to IMPs.
- Whether and when blinding was broken.

All additional information concerning the adverse event until trial termination or definite outcome must be communicated per follow-up report without delay.

The immediate and follow-up reports must only identify the subjects using the unique subject identifier.

The investigator must comply with applicable regulatory requirement(s) related to the reporting of SAEs to the regulatory authorities and the relevant IECs or IRBs.

### **Notification of serious adverse reactions**

All suspected adverse drug reactions related to an IMP (the tested drugs and comparators) that occur in this trial, and that are both unexpected and serious are subject to expedited reporting.

Once a year throughout the clinical trial, the sponsor will provide the member states in whose territory the clinical trial is being conducted and the IECs with a listing of all suspected unexpected serious adverse reactions which have occurred over this period and a report of the subjects' safety.

In addition, the sponsor will ensure that all reportable events are reported in compliance with applicable international and national regulatory requirements.

#### **12.4.2      Vital signs**

The vital signs comprise systolic and diastolic blood pressure, pulse rate, and respiratory rate.

Vital signs will be measured in a sitting position after resting for 10 minutes. While resting, the subject should not receive anything to drink or eat.

#### **12.4.3      Body weight**

Body weight will be measured in light clothes.

#### **12.4.4      Twelve-lead electrocardiogram**

All ECGs will be recorded in triplicate (3 readings in rapid succession no more than 2 minutes apart).

The times at which the ECGs were recorded will be documented in the eCRF.

The 12-lead ECG recordings will be performed after the subjects have been in a supine position for at least 10 minutes in a quiet environment without exciting distractions (e.g., television, video games). The recording should include a minimum of 5 heart cycles (beats).

Electrocardiographic parameters (heart rate; P, QRS, and T waves; PR, QT, and QTcF intervals), and waveform morphology will be evaluated by the investigator. The investigator will be responsible for determining the clinical relevance of any abnormality and deciding whether a subject can continue in the trial with the observed findings. The investigator will be required to comment any abnormalities with reference to any possible clinical relevance.

A central ECG reading facility will provide the results of the ECG interval measurements and an assessment and interpretation of any waveform abnormalities and other findings (e.g., conduction defects). The investigator will be informed of the results and must evaluate them in the context of the subject's characteristics. The investigator will be required to comment any abnormalities with reference to any possible clinical relevance. The investigator will also make a decision whether the subject should continue in the trial or whether further ECGs or investigations should be performed to clarify and ensure the safety of the subject.

Electrocardiograms with poor quality tracings, artifacts or doubtful findings should be repeated, if possible.

For decisions relating to subject exclusion or discontinuation of IMP, the investigator's initial evaluation will be used.

The evaluation from the central ECG reading facility will be used for the assessment and analysis of ECG parameters and for evaluation of any tendency regarding changes in ECG parameters for the final integrated clinical trial report.

The ECG measurements and the findings, if any, from the central ECG evaluation together with the overall assessment of the clinical relevance by the investigator will be captured in the database.

The original ECG recordings will be kept at the trial site.

The ECG files including the waveforms and caliper placements will be provided electronically as xml files to the sponsor at the end of the trial.

